5.4 Secondary Analyses of Primary Outcome Measure

Subsequent analyses will explore the treatment effect as a function of time, stratification variables and other factors that may have differential impact on treatment success. The analyses will first model the time to event primary outcome measure as a function of treatment assignment (XR-NTX vs. BUP-NX), opioid dependence severity stratum, site, and the two way treatment interaction terms (site by treatment and stratum by treatment) in a proportional hazards regression model. The Cox model previously described in the primary outcome analysis can separately incorporate covariates that are fixed (at baseline). The constancy of the relative hazard assumption will be examined via the interaction of treatment and time, and the interaction between treatment and baseline severity will be tested.

If treatment by site interaction is significant, we will further investigate if the interaction is quantitative or qualitative. A quantitative interaction between treatment and site will indicate that the treatment differences are in the same direction across sites but the magnitude differs from site to site, while a qualitative interaction reveals that substantial treatment differences occur in different directions in different sites. As indicated by Gail and Simon (1985), the existence of a quantitative interaction between treatment and site does not invalidate the analysis in pooling data across centers. Hence we will analyze the data ignoring the treatment-by-site interaction. But when there is a qualitative interaction the treatment effect itself would not make any sense and any kind of analysis claiming a common treatment effect will be questionable.

If the stratum by treatment interaction has a p-value <0.10, then this will be taken to indicate differences in strata-specific efficacy. We note that if this interaction is qualitative (i.e., reversal of treatment advantage in the subgroups) this will have important consequences for future treatment and research decisions. We will test the pair-wise differences between XR-NTX and BUP-NX, separately in the low dependence vs. high dependence subgroups, and further examine the differences with an ordinal/continuous dependence covariate. Note that we are not powering the study to detect the interaction; however, given the likelihood that baseline use predicts outcome, or may interact with treatment (Nunes et al 2011), the coefficient of the main effect of treatment in the model is not meaningful in the presence of an interaction with baseline covariates, and that a significant interaction should prompt testing of the region(s) of the baseline covariate where the probability of treatment successes differ (Nunes et al 2011; Pocock et al 2002).

Secondary analyses of the 24 week successes will include screening baseline variables to identify potential subgroups in the treatment groups with differential results.

All participants who were randomized will be included in the primary efficacy analysis. Note that the primary analysis for the time to relapse inference is based on the assumption that all missing UDSs' are positive.

A secondary analysis of the primary outcome measure will also be presented assuming these observations are censored which will allow us to assess robustness of conclusions to the deviation from the MAR missing data assumption. See Section 6.0 for additional details.

Summary statistics for the primary outcome measure will be provided for each CTP.

5.5 Secondary Outcomes

Most secondary outcome analyses will follow a similar form and strategy to that above, with different linear models as appropriate for the form of the secondary outcome variable: dichotomous secondary outcomes will use logistic regression; time-to-event variables will use survival analysis with Cox models; continuous variables or count variables (e.g., bags per day of heroin use) will use mixed effect models depending on the distribution of the outcome (e.g., normal, Poisson, negative binomial, zero-inflated). Repeated measures will have time in the model in addition to treatment and baseline covariates.

For the secondary outcome measures that are continuous a mixed effects model will be used to analyze the data incorporating appropriate covariates. The model for secondary outcomes that are continuous can be explained in matrix form as follows:

$$\begin{aligned} \mathbf{y} &= \mathbf{X}\boldsymbol{\beta} + \mathbf{Z}\mathbf{b} + \boldsymbol{\varepsilon} \\ \mathbf{b} &\sim N_q(0, \boldsymbol{\Psi}) \\ \boldsymbol{\varepsilon} &\sim N(0, \sigma^2 I) \end{aligned}$$

Where

- \mathbf{y} is the N (sample size) \times 1 secondary outcome vector.
- \mathbf{X} is the $N \times p$ model matrix for the fixed effects (e.g. Treatment).
- $\boldsymbol{\beta}$ is the $p \times 1$ vector of fixed-effect coefficients.
- \mathbf{Z} is the $N \times q$ model matrix for the random effects (e.g. Site).
- \mathbf{b} is the $q \times 1$ vector of random-effect coefficients.
- $\boldsymbol{\varepsilon}$ is the $N \times 1$ vector of errors for outcome.
- $\boldsymbol{\psi}$ is the $q \times q$ covariance matrix for the random effects.
- $\boldsymbol{\sigma}^2$ is the $N \times N$ covariance matrix for the errors.

5.5.1 Induction Success

Successful initiation of protocol medication is an important binary outcome that may also be useful to subsequently explain differences in the primary outcome. The induction success outcome will be defined as noted in Section 5.3.1. Data will be analyzed using a logistic regression model. The model will include variables for treatment arm, a continuous measure of the randomization timing and the corresponding interaction term. The continuous measure of randomization timing will be the number of days between randomization and last licit or illicit use of opioids.

5.5.2 Opioid Abstinence

Opioid abstinence will be measured using the TLFB and confirmed by urine drug screens.

5.5.3 Cigarette Smoking

Cigarette smoking is assessed by the FTND, Tobacco Use Questionnaire and visual analog scale for nicotine craving assessments.

The visual analog scale for nicotine craving is assessed at multiple follow-up timepoints and thus a mixed effects model will be used to assess whether there is a treatment effect with respect to the VAS nicotine craving scale.

5.5.4 Opioid Craving

Participants' cravings for opioid craving is documented on visual analog scales (VAS) via scores that range from 0 (no craving) to 100 (most intense craving possible). The VAS assessing opioid craving is completed at each study visit throughout the active treatment phase. A mixed effects model analysis will be conducted with treatment as a covariate.

5.5.5 Subacute Withdrawal Symptoms

Subacute withdrawal symptoms are measured by the HAM-D and the SOWS.

5.5.6 Drug Use Problems

There are two assessments that capture data on drug use problems, the ASI-Lite and the EQ-5D.

The ASI-Lite is derived from the Fifth Edition of the ASI, a structured clinical interview that yields scores for seven areas of functioning typically impacted by addiction, including medical status, employment status, drug use, alcohol use, family status, legal status, and psychiatric status. Opioid use questions, including the main type of opioid used by the participant, whether a prescription opioid or heroin, the onset of the use, the participant's perception of the substance that is most problematic, and their present treatment goal will also be assessed at screening as part of the ASI assessment. The ASI-Lite is completed at baseline, at the end-of-treatment visit (week 24/EOT), and at the week 36/EOS follow-up visit.

The seven areas of functioning measured by the ASI-Lite will be analyzed using a mixed effects model with treatment as a covariate. These seven tests will be performed without adjustment for multiple testing.

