11.4.3 Addiction Severity Index Lite (ASI-Lite)

The ASI-Lite is derived from the Fifth Edition of the ASI⁶⁸, a structured clinical interview that yields scores for seven areas of functioning typically impacted by addiction, including medical status, employment status, drug use, alcohol use, family status, legal status, and psychiatric status. Opioid use questions, including the main type of opioid used by the participant, whether a prescription opioid or heroin, the onset of the use, the participant's perception of the substance that is most problematic, and their present treatment goal will also be assessed at screening as part of the ASI assessment. The ASI-Lite is completed at baseline, at the end-of-treatment visit (week 24/EOT), and at the week 36/EOS follow-up visit.

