1.5 Randomization

Immediately following the final assessment of eligibility, participants will be randomly assigned to one of the two conditions: XR-NTX or BUP-NX. Random assignment will be on a 1:1 ratio to one of the two conditions. A restricted randomization plan will be used with centralized, automated, randomized block assignments. Randomization will be stratified by two factors, site and pre-detoxification level of opioid use. While there will be important and otherwise uncharacterized differences between sites – including state and local treatment service environments, opioid misuse epidemiology, and patient-level customs regarding treatment, medications, and clinical trial participation – the level of heroin and other opioid use will likely be an important independent predictor of treatment retention and rates of negative urines as has been demonstrated in recent analysis of naltrexone opioid trials (Sullivan et al 2006; Carpenter et al 2009; Brooks et al 2010). The level of opioid use at treatment entry is a binary classification, operationally defined as 6 or more bags (or equivalent) IV heroin per day (≥ 6 bags/day) over the 7 days prior to entry into the treatment program versus less than 6 bags (or equivalent) IV heroin per day (< 6 bags/day) or other routes of administration or other opioids.

Eligible participants will be randomized in a 1:1 ratio to the BUP-NX and XR-NTX arms. The randomization process will be performed by computer at a centralized location. Randomization will be stratified by site and pre-detoxification level of opioid use [≥ 6 or more bags (or equivalent) IV heroin per day (≥ 6 bags/day) over the 7 days prior to entry into the treatment program versus less than 6 bags (or equivalent) IV heroin per day (< 6 bags/day) or other routes of administration or other opioids]. The block size chosen will be adequate to ensure approximate treatment balance. The number in each treatment group will never differ by more than a factor of $KB/2$ where B is the block size and K is the number of strata.

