3.3 Sample Size and Power Calculations

The therapeutic strategies defined above will be evaluated and compared in a two-arm randomized open-label multi-center trial.

Original Projected Sample Size: 200 per treatment group. N = 400 total.

Data Analysis Modification Projected Total Sample Size: N~600 total sufficient to enroll 350 late randomizers.

[figure not shown]
Rationale: The primary outcome is the time to relapse as defined above. Meta-analyses of randomized controlled trials of BUP-NX maintenance treatment for opioid dependence suggest that approximately 50% of patients are retained in BUP-NX treatment with good clinical outcome over 6 months. (Mattick and Kimber 2008). Extended release naltrexone preparations have had few prior randomized comparisons but observations from a recent Russia-based trial evaluating the XR-NTX dose and formulation proposed for this trial had good results with 53% receiving all monthly injections and retained for 6 months. Direct randomized comparison of these approaches has not been performed.

We evaluate the anticipated variability of the primary terminal results by simulating under exponential distributional assumptions with event (relapse) grouping after the first 21 days and using proportional hazards without censoring. Let one treatment have a 6-month success rate of 40% with exponential failure. We use a lower success target than indicated in the above paragraph because the use of the early randomization time point is expected to increase the percentage of participants who are failures. There would be minimal impact on detectable alternatives if a higher 50% success rate was used. From the plot below, we observe that the 95% CI width for the hazard ratio for the 50th percentile of the simulation results under both the null and alternative hypotheses decreases by 31%, 19%, and 14% as the sample size increase

by 50/arm from a base of 50/arm. CI width decreases by 11% when the sample size increases from 200/arm to 250/arm. We have selected 200/arm as subsequent precision improvements with these criteria are close to 10% per 100 sampling units.

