3.5 Software

All analyses will be performed utilizing SAS® version 9.3. All statistical tests will be conducted at the 5% Type I error rate (two-sided). When multiple tests are conducted, the chance of finding a significant difference in one of the tests, when in fact no difference exists, is greater than the stated Type I error rate. The investigators are aware of the multiple testing issues and will interpret results with caution and use confidence intervals where possible.

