5.5.7 HIV Risk Behavior as Assessed by the RAB

The sex risk scale of the RAB, which produces a score ranging from 0-28, will be considered as a continuous response variable, and treatment effect will be analyzed using mixed effects model.

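### The models for opioid craving, ASI-Lite and RAB sex risk never name the outcome's own pre-treatment score as a covariate, although it is already collected

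*SAP*

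**What the plan says.** The three endpoint subsections are short.

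- **ASI-Lite (SAP 5.5.6):** "The seven areas of functioning measured by the ASI-Lite will be analyzed using a mixed effects model with treatment as a covariate".
- **Opioid craving VAS (SAP 5.5.4):** "A mixed effects model analysis will be conducted with treatment as a covariate".
- **RAB sex risk (SAP 5.5.7):** the score is treated as continuous and "treatment effect will be analyzed using mixed effects model". No covariates are listed.

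The parent section, SAP 5.5, adds a general rule: "Repeated measures will have time in the model in addition to treatment and baseline covariates". It also says that continuous outcomes use a mixed model with appropriate covariates and that most secondary analyses follow a strategy like the primary one. Its matrix model gives treatment as the example of a fixed effect and site as the example of a random effect. Protocol 12.4 carries the same rule on time and baseline variables. Neither place lists which baseline variables are meant.

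All three outcomes have a pre-treatment score. For ASI-Lite, "The ASI-Lite is completed at baseline, at the end-of-treatment visit (week 24/EOT), and at the week 36/EOS follow-up visit". Protocol 11.4.4 puts opioid craving at screening and at each study visit. Protocol 11.4.8 puts the RAB at baseline and weeks 12, 24 and 36.

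**The concern.** The primary Cox model in SAP 5.3.3 lists every term: treatment, timing, site, severity stratum and the treatment-by-timing interaction. SAP 5.5.1 lists the terms for induction success. The three subsections here do not. An analyst reading only 5.5.6 would fit treatment alone. One reading 5.5 would add time and some baseline variables, but would have to guess which. The outcome's own earlier value is the natural candidate and is never mentioned.

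The plan already accepts the principle. SAP 3.3 notes that including baseline severity in the model may raise power and narrow confidence limits. For these outcomes the pre-treatment score is on the same scale as the response, so it would be expected to explain some of the later variation. What is at stake is the width of the intervals for two superiority hypotheses (craving and drug-related problems) and one equivalence hypothesis (HIV risk), as set out in SAP Table 1.

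**Working it through.** **The plan's own power figure.** The documents give no power, SD or effect size for these three outcomes. The only stated power is for the primary logrank test (SAP Table 2: 200 per arm, 40% reference success, two-sided 5%). It reproduces with Freedman's formula:

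- HR 0.633: events = 200(1 − 0.40) + 200(1 − 0.40^0.633) = 120 + 88.0 = 208.0. Power = Φ(√208.0 × 0.367/1.633 − 1.960) = 90.0%.
- HR 0.678: events = 120 + 92.5 = 212.5. Power = Φ(√212.5 × 0.322/1.678 − 1.960) = 79.9%.

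This does not carry over to the secondary outcomes, so the rest is conditional.

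**Inputs.** From the documents: two-sided 5% (SAP 3.5) and the number of post-randomization scores m, which is 2 for ASI-Lite (weeks 24 and 36), 3 for RAB (weeks 12, 24 and 36) and 24 for weekly craving. Assumed: unit variance, a constant treatment effect, 80% unadjusted power, complete data, and correlation ρ of 0.3, 0.5 or 0.7 between any two occasions (compound symmetry). Sample size cancels because power is anchored at 80%.

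**Formulas.** The contrast is the treatment effect on the mean of the m post-randomization scores.

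- Unadjusted variance: v = (1 + (m − 1)ρ)/m
- Variance adjusted for the pre-treatment score: v_adj = v − ρ²
- Adjusted power = Φ((1.960 + 0.842) × √(v/v_adj) − 1.960)

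ASI-Lite at ρ = 0.5: v = 0.75 and v_adj = 0.75 − 0.25 = 0.50, a ratio of 0.667. Then 2.802 × √1.5 = 3.431, and Φ(3.431 − 1.960) = 92.9%.

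| Outcome | ρ = 0.3 | ρ = 0.5 | ρ = 0.7 |
|---|---|---|---|
| ASI-Lite: v_adj/v | 0.862 | 0.667 | 0.424 |
| ASI-Lite: power | 85.5% | 92.9% | 99.0% |
| RAB: power | 86.7% | 94.3% | 99.4% |
| Craving: power | 90.8% | 97.3% | 99.9% |

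**Sensitivity to the correlation.** Compound symmetry makes the pre-treatment score as informative about follow-up as one follow-up is about another. Let follow-ups correlate 0.5 with each other but only 0.2 with baseline, so that v_adj = v − 0.04:

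- ASI-Lite: 0.75 to 0.71, power 82.1%
- RAB: 0.667 to 0.627, power 82.4%
- Craving: 0.521 to 0.481, power 83.0%

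The gain is then 2.1 to 3.0 points.

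**Sensitivity to the starting power.** For ASI-Lite under compound symmetry at ρ = 0.3, 0.5 and 0.7, the gain is 6.0, 17.0 and 35.4 points from 50%, and 3.7, 7.8 and 9.9 points from 90%, where it cannot exceed 10.

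**Choice of contrast.** These gains belong to the averaged post-randomization effect. If the reported contrast were week 24 alone, adjusted for baseline, its variance would be 1 − ρ² and power would be Φ(2.802 × √(v/(1 − ρ²)) − 1.960). At ρ = 0.3, 0.5 and 0.7 that gives about 66%, 80% and 95% for ASI-Lite, and 39%, 65% and 91% for craving. At ρ = 0.3 the switch more than cancels the benefit of adjustment.

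**The case against.** The strongest reply is that SAP 5.5 governs its subsections. It promises time, baseline covariates and a strategy like the primary model's, and naming treatment as a covariate does not say that it is the only one. This stands in part. A reader might infer that the plan fits these outcomes with no adjustment at all; 5.5 and Protocol 12.4 do not support that. What they leave open is which variables enter, and the outcome's own pre-treatment score appears nowhere.

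A reader might also infer that week 0 is one of the responses, so that a single treatment term is averaged over a visit with no possible effect. For ASI-Lite that would shrink the estimate to two thirds. The documents do not say this. SAP 5.5.4 describes craving during the active treatment phase, and the Week 0 columns in SAP Appendix A Tables 27 and 31 are descriptive shells. The role of week 0 is unstated, which is a reason to state it and not evidence of an error.

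The size of the gain is also open to challenge, and fairly. No correlation is given. Craving is first scored at screening, around an inpatient admission, and may predict later craving weakly. The 24-visit figure is optimistic because participants who relapse stop weekly visits (Protocol 6.1), and the sample-size section assumes only 40% success at six months.

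Finally, these are secondary outcomes without a power calculation, and SAP 3.5 already asks for cautious interpretation. That limits the weight of the point but does not remove it.

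**Conclusion.** The point holds as a gap in specification with a cost in precision. The subsections and the general rule do not match, and neither names the pre-treatment score. Under compound symmetry and 80% unadjusted power, naming it would take ASI-Lite to about 85.5%, 93% or 99% at ρ of 0.3, 0.5 or 0.7. If the pre-treatment score is only weakly related to follow-up, the gain falls to 2 to 3 points. Any single figure or fixed range for the gain would go beyond the documents.

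A reader might also infer bias. The score is measured before treatment in a 1:1 randomized trial, so leaving it out widens intervals without in itself biasing the comparison. The primary analysis is unaffected.

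**What to change.** In SAP 5.5.4, 5.5.6 and 5.5.7:

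- Add the participant's pre-treatment score on the same outcome as a fixed-effect covariate: screening for craving, baseline for ASI-Lite and RAB.
- List time, severity stratum, early/late timing and site alongside treatment, in line with SAP 5.5 and the primary model.
- State that only post-randomization scores are responses, or specify a constrained-baseline model, which also keeps participants whose pre-treatment score is missing.
- Name the overall post-randomization treatment effect as the reported contrast. Do not replace it with a week 24 contrast.
- If a power gain is mentioned, give it only as a range over assumed correlations.

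The cost is a few lines of SAP text and about one degree of freedom per model for the added score. No new data are needed.

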5.5.7 HIV Risk Behavior as Assessed by the RAB

The sex risk scale of the RAB, which produces a score ranging from 0-28, will be considered as a continuous response variable, and treatment effect will be analyzed using mixed effects model.

5.5.8 Cognitive Function

The Trails Making test Parts A and B and the Stroop test will be used to assess cognitive function.

5.6 Minority/Gender Analyses

In accordance with NIH guidelines, repeated Cox regression model analyses will be completed to determine whether treatment response was significantly affected by participant minority/gender status using an interaction term for treatment and minority/gender as appropriate.

6.0 MISSING DATA

The primary outcome in this study defines missing urines as positive opioid use. Thus, missing value imputation of the urine drug screens is not necessary for the purposes of the primary outcome.

Dropout from treatment is a typical failure mode for the treatment of opioid dependence with both XR-NTX and BUP-NX. A sensitivity analysis for the primary outcome analysis will be performed to examine the impact on the hazard ratio and its confidence limits of alternative endpoint definitions. In particular for the primary endpoint, individuals who withdraw will be considered events if they fail to provide weekly urine specimens. An alternative to the protocol definition which introduces these as censored observations will be examined. The analyses of these events can be complex as standard assumptions (missing at random) may not be plausible.

Other outcome variables (opioid and other substance use over time, craving, mood, etc.) will have missing data due to missed visits and dropout from treatment and from study participation. The generalized linear model, or mixed effects model frameworks that will be used for analyses, works with what data are gathered, and assumes missing data are missing at random. For selected secondary outcome analyses, sensitivity analyses will be considered to examine the stability of estimated treatment effects in the face of departures from the assumption of missing at random.

